### 8.1.2 Accuracy between G6PD activity and hemoglobin methods

Quantitative agreement for both G6PD activity and Hb values between the SD Biosensor POC G6PD test and the Pointe Scientific assay will be graphically analyzed. Correlation graphs between the POC G6PD test and the Pointe Scientific assay will be plotted, and an R squared value will be determined. The following R squared values will be considered acceptable:

1. STANDARD G6PD test G6PD activity on capillary vs reference assay on venous blood > 0.8
2. STANDARD G6PD test G6PD activity on venous vs reference assay on venous blood > 0.85
3. STANDARD G6PD test hemoglobin concentration on capillary vs reference assay on capillary > 0.75
4. STANDARD G6PD test hemoglobin concentration on venous vs reference assay on capillary > 0.90

Plots, where differences between the G6PD POC test and the Pointe Scientific assay are plotted against the Pointe Scientific assay, will be used together with the 95% limits of agreement. Acceptable limits of agreement for Hb should be within  $\pm 1.0$  g/dL (based on a 6% estimate for allowable method bias) and for G6PD activity should be within  $\pm 2.0$  U G6PD/g Hb (based on a 15% estimate for allowable method bias).

All statistical analyses will be performed using Stata 13.0.

The data comparison for the analyses is outlined in Table 4 below.

Table 3. Comparison methods.

Index test by sample type	Reference method	
	G6PD normalized for Hb (U/g Hb)	Hemoglobin concentration (g/dL Hb)
Venous	Pointe Scientific G6PD normalized for hematology analyzer Hb result from venous specimen	HemoCue ® Hb from venous specimen
Capillary		HemoCue® Hb from finger stick

Abbreviations: G6PD, glucose-6-phosphate dehydrogenase; Hb, hemoglobin.

*HemoCue* is a registered trademark of *HemoCue AB*.

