### **4.2 Inclusion and exclusion criteria**

#### **4.2.1 Patients**

Criteria for inclusion of patients:

- Age 18-65
- Healthy volunteer by self-report
- Willingness to provide consent

Criteria for exclusion of patients:

- Blood transfusion in the past 90 days by self-report
- Pregnancy by self-report

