### 8.1.3 Interim analysis

An initial portion of this data will be used to support an FDA 510k submission. Per CLSI EP09-A3 (Measurement Procedure Comparisons and Bias Estimation Using Patient Samples; Approved Guideline – Third Edition) , it is recommended that measurement validation by a manufacturer include at least 100 patient samples spanning as much of the common measuring interval as feasible. This study proposes for the FDA submission from a G6PD perspective are at least 50 specimens in the G6PD severely deficient range, at least 50 specimens in the G6PD intermediate deficient range, and at least 100 specimens in the G6PD normal range. The data for this interim analysis will come from studies in Brazil and the US. Data collection for these studies are outlined in separate study protocols. When the numbers for FDA submission are reached during the trials, a data stop will occur, and the interim data will be cleaned and locked for submission purposes. Sites and investigators will be blinded to the results of the interim data analysis. The sites will keep enrolling until the numbers required for the WHO PQ are achieved. Should any results or observations occur during the continuation of the clinical study (following data cut-off for FDA

submission) which would impact our ability to demonstrate the safety, effectiveness, or equivalence to the predicate devices the FDA will be informed, and their consultation sought.

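### Section 8.1.2 uses R squared cut-offs as acceptance criteria, but R squared does not register bias and depends on the enrolled spread; the limits of agreement only partly make up for this.

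*Combined protocol and SAP*

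**What the plan says.** Section 8.1.2 covers quantitative agreement, which is among the endpoints listed in Section 3. It plots the point-of-care test against the reference, computes R squared, and states: "The following R squared values will be considered acceptable". The four items are:

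- "STANDARD G6PD test G6PD activity on capillary vs reference assay on venous blood > 0.8"
- "STANDARD G6PD test G6PD activity on venous vs reference assay on venous blood > 0.85"
- "STANDARD G6PD test hemoglobin concentration on capillary vs reference assay on capillary > 0.75"
- "STANDARD G6PD test hemoglobin concentration on venous vs reference assay on capillary > 0.90"

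It then adds difference plots with 95% limits of agreement. One sentence begins "Acceptable limits of agreement for Hb should be within" and sets ±1.0 g/dL for Hb and ±2.0 U/g Hb for G6PD activity.

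The section does not say whether both criteria must be met or which prevails if they disagree. It gives no basis for the R squared values and no expected SD for Hb or G6PD. It plans no slope, intercept or bias at a decision level, and no confidence interval for R squared or for the limits.

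Section 8.1.1 places the primary success criterion elsewhere, on correct identification of severely deficient specimens. Sensitivity and specificity are computed at 30%, 70% and 80% of an adjusted male median taken separately for each assay.

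**The concern.** R squared measures how tightly points follow a line, not whether that line is the line of identity. Adding a constant to every reading, or multiplying every reading by a constant, leaves it exactly unchanged. If only the signal is scaled and the random error stays fixed, it moves slightly, and for an over-read it moves upward. It also depends on the spread of true values: the same device scores higher when more deficient and intermediate people are enrolled.

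Two kinds of wrong verdict on the accuracy endpoint follow. A device with moderate bias near a G6PD cut-off may be called acceptable. A device that meets the plan's own agreement limit may be called unacceptable because the volunteers were too alike. The second matters for Hb, since entry requires "Healthy volunteer by self-report". The data are meant to support regulatory submissions, so the accuracy rule should answer the question asked of it.

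**Working it through.** The R squared cut-offs come with no derivation, so there is no planned figure to reproduce. The check is whether the two sets of criteria in Section 8.1.2 agree with each other.

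**Inputs from the plan.** R squared cut-offs 0.80, 0.85, 0.75 and 0.90; limits ±1.0 g/dL and ±2.0 U/g Hb; target mix 20 deficient and 20 intermediate of 250 (Section 3.1), leaving 210 normal; interim mix of at least 50, 50 and 100 (Section 8.1.3).

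**Assumptions.** The plan gives no Hb SD, so 1.2 to 1.6 g/dL is used. It gives no male median, and Table 1 points two ways: 6/0.80 = 7.5 U/g and 4/0.30 = 13.3 U/g. The 15% basis for the G6PD limit also gives 2.0/0.15 = 13.3. I use 7.5, 10 and 13.3. Simulated values are uniform over 5–30% of the median for deficient and 30–80% for intermediate. Normals centre on 105% with CV 18%, truncated at 80%.

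**Formulas.** At zero bias the largest SD of differences is s = limit/1.96: 0.51 g/dL for Hb and 1.02 U/g for G6PD. With error in the index test only, R² = σ²/(σ² + s²), where σ is the reference SD. The smallest σ that passes cut-off c is s·√(c/(1−c)).

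**1. Hb device exactly at ±1.0 g/dL.**

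- Venous 0.90: 0.51 × √(0.90/0.10) = 1.53 g/dL (1.59 if error is split equally between methods).
- Capillary 0.75: 0.51 × √(0.75/0.25) = 0.88 g/dL (0.99 with equal error).

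| Assumed Hb SD (g/dL) | R² | Chance of failing 0.90, n = 250 |
|---|---|---|
| 1.2 | 0.847 | 1.00 |
| 1.3 | 0.867 | 0.99 |
| 1.4 | 0.883 | 0.89 |
| 1.5 | 0.896 | 0.60 |
| 1.6 | 0.908 | 0.24 |

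The 0.75 cut-off is not failed anywhere in this range. For a somewhat better device, with limits ±0.88, the chances of failing 0.90 are 0.96, 0.70, 0.29, 0.05 and 0.005.

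**2. Unbiased G6PD device exactly at ±2.0 U/g.**

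| Assumed median (U/g) | R², no deficient or intermediate | R², 20+20+210 |
|---|---|---|
| 7.5 | 0.58 | 0.84 |
| 10 | 0.71 | 0.91 |
| 13.3 | 0.81 | 0.94 |

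At 7.5 U/g the intermediate steps are 0.72 (5+5) and 0.78 (10+10), and the 50+50+100 mix gives 0.90. A second simulation with different activity distributions gave 0.61 (normals only), 0.83 (20+20+210) and 0.89 (50+50+100).

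**3. Biased G6PD devices** (median 7.5 U/g, 20+20+210, error SD 0.5).

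- 30% over-read: limits about +0.5 to +3.9. It fails ±2.0.
- Constant +1.0 U/g: limits 1.0 ± 1.96 × 0.5 = 0.02 to 1.98; R² 0.96. It passes both criteria.
- Slope 0.8, correct at the median: bias at the 30% cut-off is 0.2 × (7.5 − 2.25) = +1.05 U/g; limits −1.3 to 1.4; R² 0.93. It passes both criteria.

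With each assay's own male median, sensitivity at 30% is about 0.92 for an unbiased device with the same error SD, 0.67 for the constant shift and 0.39 for the slope of 0.8. Of 20 deficient samples that is about 18, 13 and 8 correctly classified (20 × each figure).

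**4. Width of the limit at the cut-off.** The 30% cut-off is 2.25, 3.0 or 4.0 U/g at the three medians, so 2.0 U/g is 89%, 67% or 50% of it.

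**The case against.** The strongest reply is that the limits of agreement already handle bias. They include the mean difference, and they reject the 30% over-read. A reader might infer that a device with any amount of bias passes the plan. The documents do not support that: it would require the limits to be non-binding, and Section 8.1.2 does not say so. What remains is moderate bias, as in step 3, which passes even if both criteria bind.

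A reader might also infer that the accuracy verdict reflects recruitment and not device error. That goes too far. The limits measure device error directly, and the primary criterion in Section 8.1.1 is classification. Sensitivity at 30% may well expose the step 3 devices. But it rests on about 20 deficient samples, which is a recruitment goal, and each sample is worth 5 percentage points (1/20). It would show misclassification without showing its cause. Purely proportional bias largely cancels there, because each assay has its own median.

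The G6PD figures depend heavily on the assumed median. At 10 or 13.3 U/g the planned mix passes both G6PD cut-offs. At 7.5 it passes 0.80 and misses 0.85 by 0.01. The case-mix effect therefore decides the verdict mainly if recruitment falls short.

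The Hb conflict concerns one cut-off and a device near the edge of the limit. Both sexes are enrolled and anemia is not an exclusion, so an SD above 1.53 is possible.

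Section 8.1.3 cites a guideline titled "Measurement Procedure Comparisons and Bias Estimation Using Patient Samples". A reader might infer that the plan breaches it. The protocol cites it for specimen numbers, and its analysis requirements cannot be seen here, so that inference is not made.

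**Conclusion.** The point holds in limited form. R squared is an unsuitable acceptance criterion for this endpoint, and the plan leaves its relation to the limits of agreement unstated.

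- **Too lenient.** Bias of about 1 U/g near the 30% cut-off can satisfy every G6PD criterion in Section 8.1.2. That is 1.0/2.25 = 44% of the cut-off at a 7.5 U/g median, and 1.0/4.0 = 25% for the constant shift at 13.3. The examples assume error SD 0.5 U/g.
- **Too strict.** An unbiased Hb device exactly at ±1.0 g/dL fails the venous 0.90 cut-off when the Hb SD is below 1.53 g/dL. The capillary cut-off is not affected at SDs of 1.2 to 1.6.
- **Range dependence.** For one G6PD device at ±2.0, R squared moves from 0.58 to 0.84 at a 7.5 U/g median, and from 0.81 to 0.94 at 13.3, as the 20+20 samples are added.

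The algebra is certain; the SDs, medians and activity distributions are assumptions. The primary success criterion is not affected.

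**What to change.** In Section 8.1.2:

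1. Report R squared as descriptive only and remove its acceptance values.
2. State that the limits of agreement are the binding criterion.
3. Add a regression that allows error in both methods, such as Deming or Passing-Bablok, with slope, intercept and 95% CIs.
4. Report the estimated bias with 95% CI at the 30%, 70% and 80% G6PD cut-offs and at a stated Hb level.

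While editing, reconcile the fourth R squared item with Table 3. The item pairs venous Hb with a capillary reference; the table pairs it with HemoCue on the venous specimen.

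The cost is revised wording and slightly more analysis of data already being collected, with no new samples or visits. The downside for the sponsor is that a correlated but biased device can no longer be called acceptable.

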## 5.1 Diagnostic performance assessment

### 5.1.1 Blood collection and testing procedures at the point of care

Following completion of the informed consent process, the study staff, who are trained in phlebotomy, will draw the following blood volumes:

- two 2-mL of ethylenediaminetetraacetic acid (EDTA)-anticoagulated blood
- one 4-mL tube of ethylenediaminetetraacetic acid (EDTA)-anticoagulated blood
- a finger stick sample of no more than 50  $\mu$ L obtained with lancet

The tubes will be identified using a study subject number. At the clinic site lab, study staff will conduct the SD Biosensor POC G6PD test and the POC HemoCue Hb test on both finger stick blood and on blood from the 4-mL tubes of EDTA-treated venous blood. Results of the in-clinic performed POC tests will be recorded on data collection forms. If an invalid test result is obtained from the finger stick sample, a second finger stick sample will be obtained, and a second test will be run. If an invalid test result is obtained from a second finger stick, the results will be recorded as invalid. If the participant is found to be anemic based only on the HemoCue assay, the participant will be referred to a health care provider for follow-up and case management.

Once POC tests are completed on venous blood, the remaining blood in the 4-mL EDTA tube will be stored and transported as follows:

- Prevention center will transfer samples to PATH laboratories approximately twice per week. Leftover samples will be aliquoted and stored at PATH laboratory for possible confirmatory or additional testing. Depending on availability of additional novel malaria tests, additional assays may be run on remaining samples. Samples will be aliquoted 6 x 0.5 ml of whole blood in cryogenic tubes and stored at -80°C in the freezer. Maximum storage time is 10 years after study end. This leftover sample will be stored for possible additional testing with the fluorescent spot test (FST). Appropriate permission for additional testing relating to malaria will be obtained through the consent process.
- The two 2-mL EDTA venous blood samples will be transported to the central reference lab by courier.

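### Section 8.1.2 tests the device's venous hemoglobin against a capillary reference, contrary to Table 3, and its text names Pointe Scientific as hemoglobin comparator where the endpoint and Table 3 name HemoCue

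*Combined protocol and SAP*

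**What the plan says.** Section 8.1.2 lists four R squared values that count as acceptable. Items 1 and 2 concern G6PD activity. In both, the reference is run on venous blood; the bar is 0.8 when the device is used on capillary blood and 0.85 when it is used on venous blood. Items 3 and 4 concern hemoglobin. Item 3 takes finger-stick blood for device and reference alike, with a bar of 0.75. Item 4 reads "STANDARD G6PD test hemoglobin concentration on venous vs reference assay on capillary > 0.90".

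Table 3, at the end of the same section, sets the reference for each index specimen. For hemoglobin, the venous index test is compared with HemoCue ("Hb from venous specimen") and the capillary index test with HemoCue on finger-stick blood. Section 5.1.1 has staff run "the POC HemoCue Hb test on both finger stick blood and on blood from the 4-mL tubes of EDTA-treated venous blood", so both HemoCue values will exist.

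The text of 8.1.2 names another comparator. It opens by planning to analyze "Quantitative agreement for both G6PD activity and Hb values between the SD Biosensor POC G6PD test and the Pointe Scientific assay". It then describes plots in which "differences between the G6PD POC test and the Pointe Scientific assay are plotted against the Pointe Scientific assay", and the next sentence gives the acceptable hemoglobin limits of agreement as ±1.0 g/dL. The hemoglobin endpoint in the synopsis and in section 3 names HemoCue 201+. Section 2 names only the Pointe Scientific kit after mentioning an FDA-cleared hemoglobin assay.

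**The concern.** Two statements that define how the hemoglobin endpoint is judged conflict with the rest of the plan.

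First, item 4 compares the device on venous blood with a reference on capillary blood. Any scatter between finger-stick and venous blood then counts against the device, and it does so at the strictest of the four bars. The matched reference comes from the same 4-mL tube and is the one that Table 3 names.

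Second, the text sends the hemoglobin plots to an assay that gives no hemoglobin value of its own. Each participant will have three candidate reference values: capillary HemoCue, venous HemoCue and the hematology analyzer. An analyst who follows the text would probably use the analyzer; one who follows Table 3 would use HemoCue. If the two methods differ by a constant offset, both limits of agreement move by that amount, and the ±1.0 g/dL verdict can depend on the choice.

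Section 8.1.3 says that part of the data will support an FDA 510(k) submission, and section 3.1 plans to combine the data with other evaluations. The comparator should therefore be fixed before anyone sees results.

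**Working it through.** **Step 1. Each criterion against Table 3.** The single G6PD reference cell in Table 3 is read as covering both specimen rows.

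| Item | Index specimen | Reference specimen in the item | Reference in Table 3 | Bar | Agree? |
|---|---|---|---|---|---|
| 1 (G6PD) | capillary | venous | Pointe Scientific, venous | > 0.8 | yes |
| 2 (G6PD) | venous | venous | Pointe Scientific, venous | > 0.85 | yes |
| 3 (Hb) | capillary | capillary | HemoCue, finger stick | > 0.75 | yes |
| 4 (Hb) | venous | capillary | HemoCue, venous | > 0.90 | **no** |

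Item 4 is the only one that departs from the table.

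**Step 2. Who measures hemoglobin.**
- Synopsis, section 3 and Table 3: HemoCue is the hemoglobin comparator.
- Section 8.1.2, opening and difference-plot sentences: Pointe Scientific.
- Section 7.2: hemoglobin has to be measured separately from the Pointe assay. Sections 5.1.2 and 7.2: a hematology analyzer does this.
- Sections 5.1.1 and 5.2: the reference laboratory receives venous tubes only.

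Pointe Scientific therefore cannot be the capillary reference that items 3 and 4 require. Read literally, the hemoglobin difference plots have either no comparator or the analyzer.

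**Step 3. Effect of item 4 on R squared.** The documents give no SDs, so all of the following are assumptions. Let T be the SD of true venous hemoglobin, e the HemoCue error SD, d the device error SD and c the extra finger-stick scatter SD, all independent.

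- Table 3's pairing: R² = T⁴ / [(T² + d²)(T² + e²)]
- Item 4 as written: R² = T⁴ / [(T² + d²)(T² + e² + c²)]
- Ratio of the second to the first: (T² + e²) / (T² + e² + c²)

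With T = 1.5 and e = 0.3, T² + e² = 2.25 + 0.09 = 2.34. With T = 2.0 and the same e, it is 4.00 + 0.09 = 4.09.

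| T | c | Ratio | Device at 0.92 on Table 3's pairing | Device at 0.94 |
|---|---|---|---|---|
| 1.5 | 0.2 | 2.34/2.38 = 0.983 | 0.905 | 0.924 |
| 1.5 | 0.3 | 2.34/2.43 = 0.963 | 0.886 | 0.905 |
| 1.5 | 0.4 | 2.34/2.50 = 0.936 | 0.861 | 0.880 |
| 2.0 | 0.2 | 4.09/4.13 = 0.990 | 0.911 | 0.931 |
| 2.0 | 0.3 | 4.09/4.18 = 0.978 | 0.900 (0.9002) | 0.920 |
| 2.0 | 0.4 | 4.09/4.25 = 0.962 | 0.885 | 0.905 |

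The verdict at 0.90 changes in some rows and not in others. At T = 1.5 and c = 0.4, even an error-free device (d = 0) reaches only 2.25/2.50 = 0.90, which does not exceed the bar. A constant or proportional capillary shift leaves R² unchanged; only scatter matters.

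**Step 4. Effect of the comparator on the limits of agreement.** Limits within ±1.0 g/dL require |bias| + 1.96 × SD ≤ 1.0. For a device with no bias against HemoCue and a comparator offset b (assumed), the largest SD that passes is (1.0 − b)/1.96:

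- b = 0: 1.0/1.96 = 0.51
- b = 0.1: 0.9/1.96 = 0.46
- b = 0.2: 0.8/1.96 = 0.41
- b = 0.3: 0.7/1.96 = 0.36

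An offset in the other direction could instead hide a real device bias.

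**The case against.** The best defence is that the section nearly corrects itself. It refers the reader to the comparison table (calling it Table 4, although its caption is Table 3). That table sets specimen and comparator for every pair and agrees with the endpoint and with the collection procedure. A careful analyst would probably treat item 4 as a one-word slip. For the correlations, items 3 and 4 ask for a capillary reference, which only HemoCue can supply, so the list itself rules out Pointe Scientific. All the values are collected, so either comparison can still be computed and nothing is lost.

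Much of this is fair, and it limits the seriousness. It does not remove the conflict: nothing says that the table overrides a numbered acceptance criterion, and nothing in the difference-plot sentence rules out the analyzer.

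One supporting argument deserves little weight. The G6PD items give the mixed-specimen pair the lower bar, while the hemoglobin items give it the higher one, which hints at a slip. But the bars also follow the index specimen, with capillary lower (0.8 and 0.75) and venous higher (0.85 and 0.90), and on that reading item 4 is not out of line. The case rests on the contradiction with Table 3.

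The illustrations are also open to challenge. They depend on assumed SDs, and the example devices sit just above the bar, where a change of verdict is most likely. A wider hemoglobin range weakens the effect, as the T = 2.0 rows show; a narrower one strengthens it. The section 2 sentence is peripheral, since it sets no criterion.

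**Conclusion.** The concern holds. Item 4 and the hemoglobin comparator in the text of 8.1.2 are wrong as written, given Table 3, the stated endpoint and the description of the kit. That conclusion rests on the text alone and needs no assumption. That 'capillary' in item 4 was meant to be 'venous' is a likely reading, but the documents do not confirm it.

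The practical size is uncertain. Under the assumptions shown, item 4 lowers R squared by a factor between 0.936 and 0.990, enough to fail a device that would otherwise narrowly pass but not in every case. An offset of up to 0.3 g/dL between comparators would reduce the SD that passes the hemoglobin limits from 0.51 to 0.36.

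The reach is limited to the hemoglobin accuracy endpoint. G6PD items 1 and 2, sensitivity and specificity, and the primary success criterion in section 8.1.1 are untouched, and no rule makes item 4 decide overall success. It should be corrected, but it does not threaten the main result.

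**What to change.** - In item 4 of 8.1.2, make the reference HemoCue on venous blood, and have the sponsor confirm that 0.90 was intended for that pair.
- In the correlation and difference-plot text of 8.1.2, name HemoCue, matched by specimen type as in Table 3, as the hemoglobin comparator, including for the ±1.0 g/dL limits. Keep Pointe Scientific for G6PD activity only.
- In section 2, name HemoCue as the hemoglobin assay.
- Correct the pointer in 8.1.2 so that it refers to Table 3.

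The cost is wording only. HemoCue is already run on both specimens, so no further samples, tests or participants are needed. The change should be made before the interim data are locked under section 8.1.3.

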### 8.1.3 Interim analysis

An initial portion of this data will be used to support an FDA 510k submission. Per CLSI EP09-A3 (Measurement Procedure Comparisons and Bias Estimation Using Patient Samples; Approved Guideline – Third Edition) , it is recommended that measurement validation by a manufacturer include at least 100 patient samples spanning as much of the common measuring interval as feasible. This study proposes for the FDA submission from a G6PD perspective are at least 50 specimens in the G6PD severely deficient range, at least 50 specimens in the G6PD intermediate deficient range, and at least 100 specimens in the G6PD normal range. The data for this interim analysis will come from studies in Brazil and the US. Data collection for these studies are outlined in separate study protocols. When the numbers for FDA submission are reached during the trials, a data stop will occur, and the interim data will be cleaned and locked for submission purposes. Sites and investigators will be blinded to the results of the interim data analysis. The sites will keep enrolling until the numbers required for the WHO PQ are achieved. Should any results or observations occur during the continuation of the clinical study (following data cut-off for FDA

submission) which would impact our ability to demonstrate the safety, effectiveness, or equivalence to the predicate devices the FDA will be informed, and their consultation sought.

